4.6.3 Study Discontinuation

The Sponsor has the right to terminate this study at any time. Reasons for terminating the study may include, but are not limited to, the following:

- The incidence or severity of adverse events in this or other studies indicates a potential health hazard to patients
- Patient enrollment is unsatisfactory

The Sponsor will notify the investigator if the Sponsor decides to discontinue the study.

4.6.4 Site Discontinuation

The Sponsor has the right to close a site at any time. Reasons for closing a site may include, but are not limited to, the following:

- Excessively slow recruitment
- Poor protocol adherence

- Inaccurate or incomplete data recording
- Non-compliance with the International Council for Harmonization (ICH) guideline for Good Clinical Practice
- No study activity (i.e., all patients have completed the study and all obligations have been fulfilled)
- Commercial availability of PRM-151

5. **ASSESSMENT OF SAFETY**

PRM-151 is not approved and clinical development is ongoing. The safety plan for patients in this study is based on clinical experience with PRM-151 in completed and ongoing studies. The anticipated important safety risks for PRM-151 are outlined below. Refer to the PRM-151 Investigator's Brochure for detailed safety information.

Several measures will be taken to ensure the safety of patients participating in this study. Eligibility criteria have been designed to exclude patients at higher risk for toxicities. Patients will undergo safety monitoring during the study, including assessment of the nature, frequency, and severity of adverse events. In addition, guidelines for managing adverse events, including criteria treatment interruption or discontinuation, are provided below.

If patients have been prescribed pirfenidone or nintedanib, this should comply with local prescribing information. Patients should adhere to the instructions and recommendations stated in the respective local labels. Investigators should consult local prescribing information for management of AEs, including guidance on dose reductions and discontinuation of these treatments.

In exceptional circumstances, if patients cannot attend a study site for a scheduled visit, patients should be followed up ideally by telephone around the time of the scheduled visit, to collect information on any AEs and changes to concomitant medications.

Pandemic Preparedness

Patients with active infection are excluded from study participation. In the setting of a pandemic or epidemic, screening for infections prior to and during study participation should be *considered* according to local or institutional guidelines or those of applicable professional societies.

5.1 **POTENTIAL RISKS ASSOCIATED WITH PRM-151**

Potential risks for PRM-151 include infusion-related reactions (IRRs), anaphylactic and hypersensitivity reactions, *post-implantation fetal loss*, and immunogenicity. Outlined below is the safety plan for managing the potential risks of IRRs, anaphylactic and hypersensitivity reactions, *and post-implantation fetal loss*. Please refer to the latest IB for further information.

Infusion-related reaction (see Section 5.4.5.1) is a temporal and causality-based event. This is not a clinical syndrome or medical concept and cannot be characterized by clinical criterion. Whereas, hypersensitivity reaction is considered as an immune related reaction which can be immediate or delayed. There is a great degree of overlap in signs and symptoms between IRR and hypersensitivity reaction. Investigators should use their medical judgement to assess if an event is immune mediated.

5.1.1 Infusion-Related Reactions

Infusion-related reaction risks associated with PRM-151 are inherent in it being the recombinant form of a naturally-occurring human protein. PRM-151 has an endogenous counterpart and ADAs could potentially affect the efficacy of PRM-151 treatments in addition to having the potential to cross-react with endogenous hPTX-2. Patients should be monitored for IRRs, which may occur within 24 hours of administration of PRM-151.

Signs and symptoms of an infusion reaction may include the following: headache, fever, facial flushing, pruritus, myalgia, nausea, chest tightness, dyspnea, vomiting, erythema, abdominal discomfort, diaphoresis, shivers, hypertension, hypotension, lightheadedness, palpitations, urticaria, and somnolence. Although unlikely, serious allergic reactions (e.g., anaphylaxis) may occur at any time during the infusion.

In Study PRM-151-202 (n=116), 2 patients treated with PRM-151 (2.6%) experienced IRRs during the randomized period (in Weeks 1 and 8), and 10 patients treated with PRM-151 (9.0%) during the OLE period (occurring from Study Weeks 28 to 108). All IRRs were either Grade 1 or 2, except for one Grade 3 IRR.

If a patient experiences a suspected and/or non-serious hypersensitivity reaction, the case should be discussed with the Medical Monitor prior to continuing dosing. If a patient has signs or symptoms of an anaphylactic or serious hypersensitivity reaction, administration of the study drug must be discontinued permanently.

The patient should be treated according to the SOC for management of anaphylaxis or hypersensitivity reaction.

5.1.3 Post-implantation Fetal Loss

In a rabbit dose range finding embryo fetal development study, PRM-151--related adverse effects at 60 mg/kg/day included a high number of embryo-fetal deaths, post-implantation loss rate, high placental remnant rate, and lower fetal viability rate. At 200 mg/kg/day, PRM-151 treatment resulted in complete post-implantation fetal loss.

No pregnancies have been reported across any of the completed Phase 1 and 2 studies with PRM-151.

In this study, women of childbearing potential (WOCBP) must remain abstinent or use contraceptive methods with a failure rate of < 1% per year during the treatment period and for 8 weeks after the final dose of PRM-151. Male subjects with a female partner of childbearing potential or pregnant female partner must remain abstinent or use a condom during the treatment period and for 8 weeks after the final dose of PRM-151.

5.1.4 Management Guidelines for Infusion Related Reactions, and Anaphylactic and Hypersensitivity Reactions

If an IRR Grade ≥ 2 event occurs the steps outlined in [Table 2](#) should be followed. For Grade 1 IRRs, investigators should treat as per medical judgement or local procedures.

Table 2 Actions if an Infusion-Related Reactions (Grade ≥2) Occurs

Event	Actions
IRR Event Occurs	
If NCI CTCAE Grade 2 (Section 5.4.3) signs and symptoms are present:
 
 • Treat per local guidelines • Reduce rate of study drug infusion (to 120 minutes) • Collect ECG and after patient stabilizes, collect labs (serum tryptase ^c, ADA, PK sample, complement C3) • Capture signs and symptoms per Sampson criteria 
If NCI CTCAE Grade 3 signs and symptoms are present:
 
 • Treat per local guidelines • Stop study drug infusion • Collect ECG and after patient stabilizes, collect labs (serum tryptase ^c, ADA, PK sample, complement C3). • Capture signs and symptoms per Sampson criteria 
If NCI CTCAE Grade 4 signs and symptoms are present or a patient experiences a second occurrence of a Grade 3 IRR, in addition to the above guidance for a Grade 3 IRR event: ^b
 
 • Permanently discontinue study drug treatment.
IRR (Grade 2 and Grade 3 [1 occurrence]) resolved after treatment and/or reduced infusion rate	
 • Complete study drug infusion at reduced rate (120 minutes) • Closely monitor patient
IRR not resolved after treatment and/or reduced infusion rate	
 • Stop study drug infusion. • Treat and closely monitor patient
IRR (Grade 2 and Grade 3 [1 occurrence]) resolved after continued treatment	
 • Restart study drug infusion at reduced rate (120 minutes). • Next study drug infusion should be at reduced rate and pre-medication should be used. ^a • Subsequent study drug infusions may be at reduced rate with premedication. • Please note, if a patient experiences a second occurrence of a Grade 3 IRR or a Grade 4 IRR event, study drug treatment must be permanently discontinued.

ADA=anti-drug antibody; IRR=infusion-related reaction; PK=pharmacokinetics; NCI CTCAE=National Cancer Institute Common Terminology Criteria for Adverse Events.

^a Diphenhydramine or clemastine and dexamethasone are recommended (see details in text below).

^b The first occurrence of the Grade 3 IRR can be either in the Phase II Study PRM-151-202, Phase III Study WA42293, or in this Study WA42294.

^c Serum tryptase should be collected between 1 and 6 hours after the event

The next study drug infusion after a Grade ≥ 2 IRR or non-serious hypersensitivity reactions should be infused over 120 minutes and the following premedications are recommended for all subsequent study drug administrations after these events:

- Diphenhydramine 50 mg IV or clemastine 2 mg IV (or an equivalent dose of an antihistaminic drug)
- Dexamethasone 10 mg IV (or an equivalent dose of a long acting corticosteroid)

If subsequent infusion(s) are uneventful, the investigator may resume 50–70 minute infusions of study treatment and may discontinue premedication.

Suspected IRRs (Grade ≥ 2), anaphylactic, and hypersensitivity (all grades) reactions must be reported as an Adverse Event of Special Interest as described in Section 5.3.3. See reporting of IRRs discussed in Section 5.1.1.

Assessment of potential anaphylaxis will be conducted at every infusion per the clinical criterion for diagnosing anaphylaxis as described by Sampson et al. 2006 NIAID/FAAN (Appendix 5). Patients experiencing suspected anaphylaxis or hypersensitivity reaction should be managed as per local guidelines. If a patient experiences a suspected anaphylaxis and/or hypersensitivity reaction regardless of seriousness or severity, an ECG should be collected after the patient stabilizes. Blood samples for ADA, serum tryptase, complement C3, and PK analysis should be obtained at the time of the event whenever possible (serum tryptase should be collected between 1 and 6 hours after the event), and a blood sample for ADA, serum tryptase, and complement C3 should be obtained at the first follow-up visit after the event.

All potential anaphylaxis cases reported by investigators to the Sponsor will be subsequently submitted for adjudication to an Anaphylaxis Adjudication Committee composed of external experts in allergic diseases. The Committee will assess whether the reported event is a true anaphylaxis event (based on Sampson's criteria) and whether the reported anaphylaxis event is causally related to PRM-151.

If a patient has signs or symptoms of an anaphylactic or serious hypersensitivity reaction (including events deemed to have met the criteria as described by Sampson according to the blinded Anaphylaxis Adjudication Committee), administration of the study drug must be discontinued permanently.

Anaphylaxis adjudication process has been outlined in the Anaphylaxis Adjudication Committee Charter.

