4.2 METHOD OF TREATMENT ASSIGNMENT AND BLINDING

4.2.1 Treatment Assignment

In this study all patients in Cohorts A and B will receive PRM-151.

Patients enrolling in Cohort A will receive three loading doses of open-label PRM-151 on Days 1, 3, and 5, followed by Q4W infusions.

For patients enrolling in Cohort B:

- Patients previously randomized to **placebo** in Study WA42293 will receive three loading doses on Days 1, 3, and 5 in a blinded fashion. All three doses will contain PRM-151.
- Patients previously randomized to **PRM-151** in Study WA42293 will receive three loading doses on Days 1, 3, and 5 in a blinded fashion. First of the three doses will contain PRM-151, whereas the subsequent two doses will contain placebo.
- In order to maintain the blind to the treatment assignment of Study WA42293, all patients in Cohort B will be dosed in a blinded fashion on Days 1, 3, and 5 of the initial loading dose (see [Figure 3](#)).

If the first loading dose in patients in Cohort B is delayed and occurs more than 3 weeks (21 days) after the Week 52 visit in Study WA42293, patients will receive all three loading doses with PRM-151 (in a blinded fashion).

To minimize bias in this study, patients and the evaluating physicians will be blinded to treatment assignment of Study WA42293 until all patients have either completed the study or discontinued early from the study, the Study WA42293 database is locked, and the Study WA42293 analyses are final.

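### Section 5.1.4 lets the slow rate and premedication be dropped after uneventful infusions that may have been placebo, so some Day 1 reactors in Cohort B can meet PRM-151 again at Week 4 without either

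*Protocol*

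**What the plan says.** Protocol Section 5.1.4 and its Table 2 cover what follows a Grade 2 or higher IRR; the text below the table adds non-serious hypersensitivity reactions. Table 2 says of the following infusion: "Next study drug infusion should be at reduced rate and pre-medication should be used". For later ones it is only permissive: "Subsequent study drug infusions may be at reduced rate with premedication". The text below the table also sets 120 minutes for the next infusion. On premedication it is firmer than the table: "premedications are recommended for all subsequent study drug administrations after these events". The step-down clause comes last: "If subsequent infusion(s) are uneventful, the investigator may resume 50–70 minute infusions of study treatment and may discontinue premedication". It sets no condition on what the uneventful infusion contained.

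Section 4.2.1 describes the blinded loading doses of Cohort B patients who had PRM-151 in WA42293: "First of the three doses will contain PRM-151, whereas the subsequent two doses will contain placebo". Footnote c of Appendix 1 agrees. If the first dose comes more than 21 days after the WA42293 Week 52 visit, all three doses are PRM-151. They are also all PRM-151 for former-placebo patients and for Cohort A. From Week 4, every infusion is open-label PRM-151 (Sections 3.1.1 and 3.3.2).

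Section 4.3 classes placebo as an investigational product, and Appendix 1 lists Days 3 and 5 in its study drug dosing row.

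**The concern.** A step-down rule of this kind works as a rechallenge. The patient meets the drug again under precautions, and the precautions are lifted if nothing happens. That logic needs the drug to be in the bag. For one group the two infusions after Day 1 contain none, and the blind prevents the site from knowing which of its patients are in that group.

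What is at stake is patient safety at one infusion, Week 4. A patient who reacted to PRM-151 on Day 1 could be given it again over 50–70 minutes without premedication, on the strength of two placebo infusions. No endpoint, estimate or analysis in the SAP depends on this.

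**Working it through.** No formula and no stated figure apply. The check follows the rule through the loading schedule.

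**Reactions in scope.** Grade 2 IRR, first Grade 3 IRR, or non-serious hypersensitivity, on Day 1. A Grade 4 IRR, a second Grade 3 IRR, anaphylaxis and serious hypersensitivity lead to permanent discontinuation (Sections 4.6.1 and 5.1.4). Grade 1 IRRs are left to medical judgement.

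**Content of the infusions** (Sections 3.1.1 and 4.2.1; Appendix 1, footnote c):

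| Group | Day 1 | Day 3 | Day 5 | Week 4 | PRM-151 infusions after Day 1 and before Week 4 |
|---|---|---|---|---|---|
| Cohort B, former active, start within 21 days | PRM-151 | placebo | placebo | PRM-151 | 0 of 2 |
| Cohort B, former placebo | PRM-151 | PRM-151 | PRM-151 | PRM-151 | 2 of 2 |
| Cohort B, start after more than 21 days | PRM-151 | PRM-151 | PRM-151 | PRM-151 | 2 of 2 |
| Cohort A | PRM-151 | PRM-151 | PRM-151 | PRM-151 | 2 of 2 |

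**Trace for the first row.**
1. Day 1, PRM-151: a qualifying reaction occurs.
2. Day 3, placebo: this is the next infusion, so it runs over 120 minutes with premedication.
3. Day 5, placebo: if Day 3 was uneventful, the precautions may already be relaxed, since the clause can be read as needing only one infusion. If two are needed, Day 5 supplies the second.
4. Week 4, PRM-151: on either reading the condition has been met, and the infusion may run over 50–70 minutes without premedication.

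**Interval to the next PRM-151 infusion.** Day 1 to Week 4 is 28 days. With the ±5-day window it is 28 − 5 = 23 to 28 + 5 = 33 days.

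**Exception.** If the IRR resolves, Table 2 has the Day 1 infusion completed or restarted over 120 minutes, which gives some same-day re-exposure to PRM-151. That belongs to the Day 1 infusion and is not a subsequent one. It offers nothing when the reaction does not resolve or begins after the infusion has ended. Section 5.1.1 allows for late onset: "Patients should be monitored for IRRs, which may occur within 24 hours of administration of PRM-151".

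**Number affected.** Not derivable. Section 5.1.1 gives only any-grade IRR patients from Study PRM-151-202: 2 (2.6%) in the randomized period and 10 (9.0%) in the extension, with one Grade 3 event overall. There is no Day 1 rate for Grade 2 or higher, and the size of the former-active group is not stated.

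**The case against.** **Placebo infusions are not worthless evidence.** A reader might infer that Days 3 and 5 tell the investigator nothing. The documents do not support that. The placebo has the same buffer, sorbitol, polysorbate and pH as PRM-151 and is matched in volume (Sections 4.3.1.1 and 4.3.1.2). In the Phase II randomized period, IRRs occurred in 2 PRM-151 patients and 1 placebo patient, 2.6% in each arm (Section 1.3.1), although these numbers are very small. An uneventful placebo infusion does test the vehicle and the procedure. It is silent only on the protein. This stands, and it narrows the point.

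**The rule permits relaxation and does not order it.** A reader might infer that the protocol directs sites to drop the precautions. It does not. Premedication is the recommended default until someone stops it. The investigator, though blind to the parent arm, knows from the protocol that Days 3 and 5 may be placebo and that Week 4 is PRM-151. This also stands.

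**Other safeguards apply at Week 4.** These are at least 1 hour of observation after the infusion and a Sampson assessment after every infusion (Section 4.3.2), vital signs every 15 minutes during it (Section 4.5.5), and toxicity and stability checks before dosing (Sections 4.5 and 5.1.2). Medical Monitor discussion is required after hypersensitivity (Section 5.1.2) and before suspended treatment resumes (Section 5.2.2). Adverse events of special interest are reported within 24 hours (Section 5.3.3), and the data monitoring committee reviews unblinded safety data until WA42293 is unblinded (Section 5.8). So the patient is not unmonitored. But none of these sets the infusion rate or premedication at Week 4, and an IRR patient who stays on schedule triggers neither Medical Monitor discussion.

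**The terms may mean PRM-151 only.** Section 6 sometimes speaks of PRM-151 study drug, and the infusion time in Section 4.3.2 is stated for PRM-151. Against that, Section 4.3 and Appendix 1 count placebo as study drug, and Section 3.1.1 applies the same infusion time to placebo loading doses. The wording is at best ambiguous, and a blinded site could not apply the narrower reading anyway. The pharmacy manual and Investigator's Brochure could add instructions, but they are not available here.

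**Conclusion.** The point holds in a limited form. Section 5.1.4 permits, without requiring, a return to 50–70 minutes without premedication on evidence that may come from placebo alone. This affects only former-active Cohort B patients who start within 21 days of the WA42293 Week 52 visit and have a qualifying reaction on Day 1. For them, 0 of 2 infusions between Day 1 and Week 4 contain PRM-151, and the next PRM-151 infusion is 23–33 days away, apart from any same-day completion or restart.

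The conclusion assumes that Days 3 and 5 are given as scheduled; a missed loading dose leads to reloading, which is a different case. It also assumes that placebo infusions can count under the clause, as Section 4.3 and Appendix 1 suggest.

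It would go too far to infer a defect for Cohort B as a whole: former-placebo patients and delayed starts are rechallenged with PRM-151 on Days 3 and 5, as is Cohort A. Nor can a rate of harm be inferred, since the documents give no basis for a count. No planned estimate changes. This is a cheap safety improvement, worth considering.

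**What to change.** Add to Section 5.1.4 and Table 2, by amendment or safety letter to sites, wording such as:

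> For Cohort B patients whose first loading dose falls within 21 days of the WA42293 Week 52 visit, whichever arm they were in, the blinded Day 3 and Day 5 infusions do not count towards the step-down rule. After a qualifying reaction on Day 1, keep the 120-minute rate and the recommended premedication through at least the first open-label PRM-151 infusion (Week 4), and relax only if that infusion is uneventful.

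Covering both parent arms keeps the WA42293 blind. Cohort A and starts delayed beyond 21 days keep the present rule. Delayed starts can be identified from dates, so exempting them does not threaten the blind. Premedication remains a recommendation.

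**Cost.** No extra visits. A Day 1 reactor would have three infusions under precautions (Days 3 and 5 and Week 4). The present text already calls for Day 3, so the increment is at most 3 − 1 = 2. Each slow infusion is 120 − 70 = 50 to 120 − 50 = 70 minutes longer, or 100–140 minutes for two. Where premedication would otherwise have been stopped, two infusions add at most 2 × 10 = 20 mg of IV dexamethasone, plus an antihistamine each time.

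Former-placebo reactors bear this too, although their Day 3 and Day 5 infusions already test PRM-151. Their number cannot be derived, and they could be a large share of Day 1 reactors. That is the price of keeping the blind.

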5.2 MANAGEMENT OF PATIENTS WHO EXPERIENCE ADVERSE EVENTS

5.2.1 Dose Modifications

Dose modifications of PRM-151 or matching placebo are not permitted in the study.

5.2.2 Treatment Interruption

Study treatment may be temporarily suspended in patients who experience toxicity considered to be related to study drug. Resumption of study treatment should be discussed with the Medical Monitor.

In the event that one or more doses of study treatment is missed, the patient will be required to reload with three doses of study treatment at the next scheduled visit, allowing alternate days between infusions. Reasons for any such dose interruptions should be recorded in the eCRF. The investigator should discuss with the Medical Monitor prior to reloading after a dose is missed due to an adverse event.

5.3 SAFETY PARAMETERS AND DEFINITIONS

Safety assessments will consist of monitoring and recording AEs, including SAEs and adverse events of special interest, performing protocol-specified safety laboratory assessments, measuring protocol-specified vital signs, and conducting other protocol-specified tests that are deemed critical to the safety evaluation of the study.

Certain types of events require immediate reporting to the Sponsor, as outlined in Section [5.5](#).

5.3.1 Adverse Events

According to the ICH guideline for Good Clinical Practice, an AE is any untoward medical occurrence in a clinical investigation subject administered a pharmaceutical product, regardless of causal attribution. An AE can therefore be any of the following:

- Any unfavorable and unintended sign (including an abnormal laboratory finding), symptom, or disease temporally associated with the use of a medicinal product, whether or not considered related to the medicinal product
- Any new disease or exacerbation of an existing disease (a worsening in the character, frequency, or severity of a known condition) (see Sections [5.4.5.9](#) and [5.4.5.10](#) for more information)
- Recurrence of an intermittent medical condition (e.g., headache) not present at baseline
- Any deterioration in a laboratory value or other clinical test (e.g., ECG, X-ray) that is associated with symptoms or leads to a change in study treatment or concomitant treatment or discontinuation from study drug
- AEs that are related to a protocol-mandated intervention, including those that occur prior to assignment of study treatment (e.g., screening invasive procedures such as biopsies)

